### Primary Analysis for Primary Efficacy Endpoint

The primary analysis on the primary efficacy endpoint will be conducted in Part 2 using the modified intent-to-treat (mITT) population. A restricted maximum likelihood (REML)-based mixed-effects model for repeated measures (MMRM) will be used as the primary analysis method. The repeated measures include weekly postbaseline visits through Week 3, with the change from baseline in total sBA as the dependent variable. The MMRM model will include the fixed, continuous effects of baseline sBA and gestational age, fixed categorical effects of presence/absence of gestational diabetes, treatment group, visit, and treatment group-by-visit interaction and participant as a random effect.

The unstructured variance/covariance matrix will be used to model the variances and covariances for the time points included in the model. The unstructured variance/covariance does not impose any restrictions on the pattern of the matrix elements. The use of an endpoint 3 weeks after baseline should result in minimal amounts of missing data. Every attempt (e.g., relaxing the convergence criteria, increasing the iteration limit, choosing reasonable starting values for the estimates) will be made to ensure convergence using the unstructured modeling of within-participant correlations. However, if the numerical algorithm for estimation of the mixed model fails to converge, the following variance/covariance matrix structures will be used in the following order: 1) heterogeneous Toeplitz, 2) heterogeneous compound symmetry, and 3) heterogeneous autoregressive of order 1. The first (co)variance structure that does not have a convergence problem will be the one used for the analysis. The Kenward-Roger approximation (1997) will be used to estimate denominator degrees of freedom.

The primary efficacy analysis will compare volixibat and placebo using the contrast (difference in least squares [LS] means) between treatment groups at Week 3. Significance tests will be based on LS means using a 2-sided significance level (2-sided 95% CIs).

The null hypothesis for the primary efficacy endpoint of the equality of volixibat and placebo is:

H0: mean change in total sBA baseline and Week 3 in the 2 treatment groups are equal

The null hypothesis of equal treatment effect will be rejected if the statistical analysis results in a 2-sided p-value for treatment at Week 3 is  $\leq 0.05$ . LS means will be calculated for each treatment group for each postbaseline visit in the model. The difference between volixibat and placebo change from baseline in sBA will be estimated, with the corresponding 2-sided 95% CI constructed for each visit through Week 3. The change from baseline LS means with SE, 95% CI for the LS means, p-value for testing if the LS mean is zero, LS mean difference between treatment groups (volixibat minus placebo) with SE, 95% CI for the LS mean difference, and p-value for testing if the treatment LS means are equal will be presented.

The study will be claimed successful if the hypothesis of no treatment effect on the primary efficacy endpoint over Part 2, in the mITT population is rejected at the 0.05 (2-sided) significance level.

Separately, a similar analysis on each of the open-label cohorts will be performed. The analysis will be identical, except that baseline sBA will not be a covariate used within the model.

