## 1. PROTOCOL SUMMARY

### 1.1. Synopsis

Name of Sponsor/Company: Mirum Pharmaceuticals, Inc.	
Name of Investigational Product: Volixibat	
Name of Active Ingredient: Volixibat potassium (formerly SHP626 and LUM002)	
Protocol Number: VLX-401	
Title of Study: A Phase 2a/2b Randomized Double-Blind Placebo-Controlled Study to Evaluate the Efficacy and Safety of Volixibat in Adult Women with Intrahepatic Cholestasis of Pregnancy and Elevated Serum Bile Acid Concentrations (OHANA)	
Study Centers: This study will be conducted at multiple sites across Australia, New Zealand, North America, and the United Kingdom. Other regions may be added.	
Participants: Up to 280 participants will be enrolled in this study. 

Part 1 (open label): Up to 80 participants with serum bile acid (sBA) <math>\geq 10</math> <math>\mu\text{mol/L}</math> during the screening period or at any time during the current pregnancy will be enrolled.

Part 2 (double blind): Approximately 200 participants with a screening sBA level <math>\geq 20</math> <math>\mu\text{mol/L}</math> will be enrolled (100 per arm).

	
Randomization: Part 1 (open label): 

1:1 (volixibat 20 mg twice daily [BID]/volixibat 80 mg BID)

 Part 2 (double blind): 

1:1 (selected volixibat dose BID/placebo BID)

 Randomization will be stratified according to background use of ursodeoxycholic acid (UDCA) or not (in Part 1), gestational age at randomization, presence/absence of gestational diabetes, and highest sBA levels before randomization (in Part 2).	
Study Period: 2020 to 2024	Study Phase: 2a/2b

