### **6.3. Method of Treatment Assignment and Management**

#### **6.3.1. Randomization Procedures**

Individual participant treatment is automatically assigned by an interactive response technology (IRT) system.

- For Part 1, participants will be randomized with stratification (based on background use of UDCA or not, gestational age [ $<32$  weeks or  $\geq 32$  weeks] at randomization, and presence/absence of gestational diabetes) after confirmation of study eligibility in a 1:1 ratio via a computer-generated randomization schedule to receive volixibat 20 mg BID or 80 mg BID.
- For Part 2, a dynamic allocation method, introduced by Pocock and Simon (1975) will be adopted to balance participant assignment between treatment arms based on the following factors: gestational age ( $<32$  weeks or  $\geq 32$  weeks) at randomization, presence/absence of gestational diabetes, and highest sBA before randomization ( $<40$   $\mu\text{mol/L}$ ,  $\geq 40$   $\mu\text{mol/L}$  to  $<100$   $\mu\text{mol/L}$ , or  $\geq 100$   $\mu\text{mol/L}$ ) after confirmation of study eligibility in a 1:1 ratio via a computer-generated randomization schedule to receive the selected volixibat dose (determined at the interim analysis) or placebo BID

The participant's randomization number represents a unique number corresponding to the treatment allocated to the participant.

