## 10.1. Sample Size Determination

Part 1 of the study is designed for estimation without formal statistical testing; hence, there are no formal power considerations. For example, with 20 participants per group and assuming a standard deviation of 25 for each group, a 95% CI for the mean for each volixibat arm would have a half width of 11.

For the power calculations for Part 2, it is assumed that only a single dose will be selected at the end of Part 1, and a 2-sided alpha 0.05 will be used to test whether there is a difference between the 2 groups. Thus, for Part 2, a sample size of 100 participants per arm has 80% power to detect mean difference of 10 with standard deviation of 25. Power was calculated using SAS, version 9.4.

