### 3.3. Strata and Covariates

Participants will be randomly assigned to treatment groups via the interactive voice or web response system (IXRS).

- For the primary cohort, a dynamic allocation method, introduced by Pocock and Simon (1975) will be adopted to balance participant assignment between treatment arms based on the following factors: gestational age (<32 weeks or ≥32 weeks) at randomization, presence/absence of gestational diabetes, and highest sBA before randomization (<40 µmol/L, ≥40 µmol/L to <100 µmol/L, or ≥100 µmol/L) after confirmation of study eligibility. Participants with highest pre-randomization sBA <40 µmol/L shall comprise no more than 33% of the primary cohort for Part 1 and Part 2, respectively.
  - For Part 1, in a 1:1:1 ratio via a computer-generated randomization schedule to receive volixibat 20 mg BID, volixibat 80 mg BID, or placebo BID
  - For Part 2, in a 1:1 ratio via a computer-generated randomization schedule to receive the selected volixibat dose (determined at the interim analysis) or placebo BID
- For the supplemental cohort, participants will be randomized with stratification (based on gestational age at randomization and presence/absence of gestational diabetes) after confirmation of study eligibility in a 1:1 ratio via a computer-generated randomization schedule to receive volixibat 20 mg BID or 80 mg BID.

Efficacy endpoints will be evaluated using stratification factors as covariates or stratification variables for analyses, as specified in [Section 6](#). If there is an imbalance in presumed prognostic baseline characteristics between treatment groups, efficacy evaluations may be performed that include these baseline values in efficacy analysis models as covariates; these evaluations will be considered sensitivity analyses.

For efficacy endpoints, the baseline value of the efficacy variable(s) will be included as a covariate in the efficacy analysis model.

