#### **6.1.2. Estimand and Analysis of the Treatment Effect**

The estimand for the treatment effect will be the mean difference between volixibat and placebo for the change from baseline in sBA at Week 3.

The primary analysis will be conducted in the primary cohort using the modified ITT (mITT) population. A restricted maximum likelihood (REML)–based mixed-effects model for repeated measures (MMRM) will be used including weekly postbaseline change from baseline in total sBA during the core study period (double-blind treatment period) through Week 3, as the dependent variable and the fixed, continuous effects of baseline sBA and gestational age, fixed categorical effects of presence/absence of gestational diabetes, treatment group, visit, and treatment group by-visit interaction as covariates and participant as a random effect.

The unstructured variance/covariance matrix will be used to model the variances and covariances for the time points included in the model. The unstructured variance/covariance does not impose any restrictions on the pattern of the matrix elements. The use of an endpoint 3 weeks after baseline should result in minimal amounts of missing data. Every attempt (e.g., relaxing the convergence criteria, increasing the iteration limit, choosing reasonable starting values for the estimates) will be made to ensure convergence using the unstructured modeling of within-participant correlations. However, if the numerical algorithm for estimation of the mixed model fails to converge, the following variance/covariance matrix structures will be used in the following order: 1) heterogeneous Toeplitz, 2) heterogeneous compound symmetry, and 3) heterogeneous autoregressive of order 1. The first (co)variance structure that does not have a convergence problem will be the one used for the analysis. The Kenward-Roger approximation (1997) will be used to estimate denominator degrees of freedom.

The primary efficacy analysis will compare volixibat and placebo using the contrast (difference in least squares [LS] means) between treatment groups at Week 3. Significance tests will be based on LS means using a 2-sided significance level (2-sided 95% CIs).

The null hypothesis for the primary efficacy endpoint of the equality of volixibat and placebo is:

H0: mean change in total sBA baseline and Week 3 in the two treatment groups are equal

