## 8. PATIENT-REPORTED OUTCOMES

To evaluate QoL in participants with ICP-associated pruritus treated with volixibat versus placebo on the basis of the following endpoints:

- Change in 5-D Itch scale with 1-week recall from baseline to Week 3 and delivery
- Change in Clinician Scratch Scale (CSS) from baseline to Week 3 and delivery
- Change in EQ-5D-5L from baseline to Week 3 and delivery
- Change in PROMIS fatigue score from baseline to Week 3 and delivery
- Change in PROMIS sleep score from baseline to Week 3 and delivery
- Change in Patient Impression of Severity of Itch (PIS-Itch) from baseline to Week 3 and delivery
- PGIC-Itch at Week 3 and delivery

Because the PROs are administered only at baseline, Week 3, and end of treatment, the change from baseline will be compared between the two groups with use of rank ANCOVA with adjustment for baseline with the Mann-Whitney odds as the estimand. The estimates and CIs can be calculated using the R package sanon ([Kawaguchi and Koch 2015](#)).

Additionally, the difference between treatment groups in the change from baseline at Week 3 and, separately, at delivery, will be evaluated using an ANCOVA model with fixed, categorical effects of treatment group, visit, and treatment group-by-visit interaction as well as the continuous, fixed covariates of baseline and the baseline-by-visit interaction. LS means will be calculated for each treatment group in the model. The difference between volixibat and placebo change from baseline in each outcome variable will be estimated, with the corresponding 2-sided 95% CI constructed for each visit. Change from baseline LS means with standard error, 95% CI for the LS means, p-value for testing if the LS mean is zero, LS mean difference between treatment groups (volixibat minus placebo) with standard error, 95% CI for the LS mean difference, and p-value for testing if the treatment LS means are equal will be calculated for each visit. The number of observations, mean, 95% CI on the mean, standard deviation, median, minimum, and maximum on both the observed and change from baseline values will also be summarized by treatment group for each visit.

For PGIC-Itch, since the PRO is a measure of change without a defined baseline, an ANCOVA model will be used, but will not include fixed covariates of baseline and the baseline-by-visit interaction. The dependent variable will be the PGIC-Itch value.

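### The primary sBA MMRM leaves out one of the three factors Part 2 is minimised on and fits a single baseline slope for all visits. The analysis stays valid, but the Week 3 standard error may be up to about 7% wider than it need be.

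*Protocol*

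**What the plan says.** Protocol 6.3.1 allocates Part 2 by Pocock-Simon minimisation on gestational age (<32 or >=32 weeks), then "presence/absence of gestational diabetes, and highest sBA before randomization" in three levels: <40, 40 to <100 and >=100 µmol/L. SAP 3.3 gives the same factors and levels.

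The primary model in protocol 10.4.1.1 reads "The MMRM model will include the fixed, continuous effects of baseline sBA and gestational age". Its categorical effects are gestational diabetes, treatment, visit and treatment-by-visit. SAP 6.1.2 matches it: "the fixed, continuous effects of baseline sBA and gestational age", with the same categorical terms. Neither has a highest-sBA category or a baseline-by-visit interaction.

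SAP 3.3 sets a general rule: "Efficacy endpoints will be evaluated using stratification factors as covariates or stratification variables for analyses". The sentence goes on to defer to SAP Section 6, and Section 6.1.2 leaves this factor out without giving a reason.

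The ItchRO model (protocol 10.4.1.3, SAP 6.2) is described only as comparable to the primary one; its terms are not listed. In SAP Section 8, by contrast, the additional ANCOVA for the other patient-reported outcomes does include "the continuous, fixed covariates of baseline and the baseline-by-visit interaction".

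**The concern.** A factor is used in minimisation because it is thought prognostic. If it predicts the outcome and is then left out of the model, its variance stays in the residual while the allocation has balanced it. The model-based standard error is then too large and the test conservative.

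Baseline sBA covers part of this but is a different quantity. SAP 3.8.3 takes baseline as the last value on or before first dose. The minimisation factor is the highest value before randomization, which could come from an earlier sample; protocol 5.1 asks for historic or local sBA to be documented.

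The baseline slope raises a similar issue. With one slope across Weeks 1 to 3, any drift in the relation between baseline and change becomes misfit at Week 3, the only visit that decides the primary test. Protocol 4.3.2.1 expects a larger effect at Week 3 than at Week 2, so a constant slope should not be taken for granted.

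The omission may be an oversight. SAP 6.2 names gestational age, baseline ItchRO and gestational diabetes as its strata but sums over 12 of them. Twelve is 2 x 2 x 3, the minimisation factors including sBA; with the two ItchRO groups of SAP 3.4 it would be 2 x 2 x 2 = 8. That is an inference only.

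What is at stake is precision, not type I error or bias.

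**Working it through.** **1. The plan's own figure.** Protocol 10.1 specifies that "a 2-sided alpha 0.05 will be used to test whether there is a difference between the 2 groups", and that "a sample size of 100 participants per arm has 80% power to detect mean difference of 10 with standard deviation of 25". Allocation is 1:1.

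- SE of the difference = 25 x sqrt(2/100) = 3.536.
- Normal power = Φ(10/3.536 - 1.960) = Φ(0.868) = 80.7%.
- Noncentral t with 198 df: 80.4%. The normal formula needs 99 per arm.

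The 80% reproduces. It is a two-sample calculation with no covariate adjustment, so neither omission makes it wrong. The protocol does not say whether the SD of 25 is raw or already covariate-adjusted.

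**2. Analytic range.** The documents give no covariate correlations. Let R² be the assumed share of the remaining variance explained by the added terms, and treat 25 as the residual SD of the planned model. Then SE = 3.536 x sqrt(1 - R²).

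| Assumed R² | SE | Planned SE / fuller SE | Power (t) |
|---|---|---|---|
| 0 | 3.536 | 1.000 | 80.4% |
| 0.02 | 3.500 | 1.010 | 81.1% |
| 0.05 | 3.446 | 1.026 | 82.3% |
| 0.10 | 3.354 | 1.054 | 84.3% |

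**3. Simulation, to see which part of that range is plausible.** There were 600 trials per scenario with N = 200, minimised on the three factors, with three visits, unstructured covariance and complete data. All of the following are assumptions: residual SD 20; lognormal baseline and peak sBA with log-scale correlation 0.7 and peak never below baseline; a category effect of 0, 5 or 10 µmol/L per step beyond baseline; and baseline slopes at Weeks 1/2/3 that are flat (-0.3 throughout), drifting (-0.2/-0.3/-0.4) or strongly drifting (-0.1/-0.3/-0.5). Mean Week 3 SE:

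| Slopes, category effect | Planned | + category | + baseline-by-visit | Both | Planned / both |
|---|---|---|---|---|---|
| Flat, 0 | 2.828 | 2.837 | 2.827 | 2.835 | 0.998 |
| Flat, 10 | 2.900 | 2.844 | 2.899 | 2.842 | 1.020 |
| Drift, 0 | 2.874 | 2.882 | 2.839 | 2.847 | 1.009 |
| Drift, 10 | 2.930 | 2.876 | 2.894 | 2.839 | 1.032 |
| Strong drift, 0 | 2.947 | 2.956 | 2.814 | 2.822 | 1.044 |
| Strong drift, 10 | 3.029 | 2.977 | 2.895 | 2.838 | 1.067 |

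The scenarios with a category effect of 5 fall between these extremes.

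- Category alone: planned / (+ category) runs from 0.997 (2.828/2.837) to 1.020 (2.900/2.844).
- Baseline-by-visit alone: planned / (+ baseline-by-visit) runs from 1.000 (2.828/2.827) to 1.047 (2.947/2.814).
- Both: 0.998 to 1.067.

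**4. Back to the design scale.** At the favourable end, 3.536/1.067 = 3.314, giving normal power Φ(10/3.314 - 1.960) = Φ(1.058), about 85%. At the other end power stays at about 81%. A ratio of 1.02 for the category corresponds to R² = 1 - 1/1.02² = 0.039, so the 5% and 10% rows in step 2 exceed anything the simulation produced for the category alone.

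**The case against.** The case for leaving the model alone has four parts.

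- **Baseline sBA already does most of the work.** Under assumed lognormal baseline and peak values (log correlation 0.6-0.9, residual SD 25), an R² of 5% for the category needs a shift of about 9-13 µmol/L per step beyond baseline, and 10% needs about 14-19. The whole treatment effect the trial is powered for is 10. Nothing in the documents supports category effects that large. This stands, and it is why the category's share is put at 0-2%.
- **SAP 3.3 is not plainly breached.** It defers to Section 6 and allows factors to serve as covariates or as strata. SAP 3.4 also plans subgroup analyses by these factors, and SAP 3.3 allows extra covariates as sensitivity analyses if baseline characteristics are imbalanced. This stands in part: the two sections need aligning, but those secondary provisions do not alter the primary test.
- **Slope drift is not documented.** No passage shows the baseline slope changing by visit. The SAP Section 8 precedent is weak, since that model covers Week 3 and delivery, and protocol 10.4.3.1 specifies only rank ANCOVA with baseline adjustment. This stands, so the interaction is a low-cost safeguard.
- **ItchRO.** A reader might infer that the ItchRO MMRM demonstrably omits the same terms. The documents do not support that, because its terms are never listed. Protocol 2.2 also calls the direct correlation between sBA and itch severity debatable. What can be said is that the model is unspecified.

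**Conclusion.** The point holds as a modest efficiency improvement to the primary MMRM. One minimisation factor is unadjusted and one baseline slope serves all visits. Any effect is a wider interval and some lost power; there is no inflation of type I error, no bias and no change of estimand.

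Under the assumed scenarios the Week 3 SE is about 0-7% wider than with both terms. The top of that range needs both a strong category effect and strong slope drift. If peak sBA adds nothing beyond baseline and slopes are equal, there is no gain. The simulation used complete data, so it does not address missing Week 3 values.

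A reader might infer that the standard errors are certainly too wide, or that the trial is underpowered as planned. Neither follows. The loss depends on two conditions for which the documents give no data, and the 80% power was calculated without covariate adjustment and reproduces. For ItchRO the gain is unknown.

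**What to change.** Before unblinding:

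- In protocol 10.4.1.1 and SAP 6.1.2, add the three-level highest-sBA-before-randomization category as a fixed effect and a baseline sBA-by-visit interaction. Keep continuous baseline sBA and continuous gestational age.
- Align SAP 3.3 with 6.1.2 so that both name the same factors. If either term is deliberately left out, give the reason.
- Write out the ItchRO MMRM in full in protocol 10.4.1.3 and SAP 6.2: the same three minimisation factors, baseline ItchRO and baseline ItchRO-by-visit.
- Carry the terms into the MMRM refitted to imputed data (SAP 6.1.7) and the sample code in SAP Appendix 3, which has a single baseline term and no sBA category.

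For the primary model the cost is 2 degrees of freedom for the category and 2 for the interaction over three visits, about 4 in all with 200 participants. It is a wording change: no new data and no change to sample size. If the terms were added only after unblinding, they would be post hoc.

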#### Type of Participant and Disease Characteristics

3. Diagnosis of ICP, as characterized by the following:  
Onset of pruritus during pregnancy with no known etiology other than ICP (e.g., pruritic urticarial papules and plaques of pregnancy, pruritic folliculitis, uncontrolled thyroid disease, etc.)  
sBA level  $\geq 10$   $\mu\text{mol/L}$  at any point during the current pregnancy  
Absence of known pathology that may produce similar laboratory findings/symptoms; these include but are not limited to other cholestatic disorders such as PBC and PSC  
Note: Suspicion of transient hypercholanemia should be discussed with medical monitor to confirm participants eligibility.

4. Part 1:
  - sBA of  $\geq 10$   $\mu\text{mol/L}$  as assessed by the central laboratory during the screening period or local laboratory at any time during the current pregnancy
- Part 2:
  - sBA level  $\geq 20$   $\mu\text{mol/L}$  as assessed by the central laboratory during the screening period
  - Documentation of historic or local sBA level is required to confirm participant eligibility before randomization.
  - Laboratory assessments may be repeated at the investigator's discretion before randomization.
  - Participants already on UDCA at the time of the screening visit shall be eligible for Part 1.
5. Willing and able to refrain from the use of any of the following for the duration of the study: statins, rifampin, bile acid sequestrants (e.g., cholestyramine), peroxisome proliferator-activated receptor (PPAR) agonists/fibrate drugs (e.g., fenofibrate, bezafibrate), S-adenosyl methionine
  - Participants requiring local/systemic corticosteroids or selective serotonin reuptake inhibitors (e.g., sertraline) for the management of non-cholestatic, non-pruritic conditions must have been on a stable dose for at least 1 week before screening and be willing to remain on a stable dose for the duration of the study to be considered eligible.
  - Administration of isolated doses of corticosteroids for obstetric indications (e.g., promotion of fetal lung maturity for anticipated preterm delivery) is permitted
6. Part 2 only: Willing and able to enter daily patient-reported outcome (PRO) information in an eDiary for the duration of the study and completes  $\geq 70\%$  of the eDiary ItchRO assessments during the screening period. A minimum of 4 once-daily ItchRO entries are required during screening.

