## 1. INTRODUCTION

This statistical analysis plan (SAP) describes the statistical analysis methods and data presentations to be used in tables, figures, and listings (TFLs) for the interim analysis as well as final analysis to support the clinical study report (CSR) for Study VLX-401. This SAP is based on the study protocol Version 1, 14 October 2020, and the electronic case report forms (eCRF). The SAP will be finalized before the interim analysis.

Any deviations from the approved protocol will be documented in either [Section 6](#) (efficacy) and/or [Section 7](#) (safety).

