### **Part 1: Proof of Concept, Dose Ranging, Pharmacokinetics, and Interim Analysis**

After a screening period of up to 10 days, eligible participants will be identified for one of two cohorts, defined as follows:

- Primary cohort: Participants with ICP with a screening sBA level  $\geq 20$   $\mu\text{mol/L}$  will be randomized with stratification (based on gestational age [ $<32$  weeks or  $\geq 32$  weeks] at randomization, presence/absence of gestational diabetes, and highest sBA before randomization [ $<40$   $\mu\text{mol/L}$ ,  $\geq 40$   $\mu\text{mol/L}$  to  $<100$   $\mu\text{mol/L}$ , or  $\geq 100$   $\mu\text{mol/L}$ ]) in a 3-arm (1:1:1), double-blind fashion to receive volixibat 20 mg BID, volixibat 80 mg BID, or placebo.
- Supplemental cohort: Up to 30 participants with ICP with screening sBA level from  $\geq 15$  to  $<20$   $\mu\text{mol/L}$  will be randomized (based on gestational age at randomization and presence/absence of gestational diabetes) in a 2-arm (1:1), open-label fashion to receive volixibat 20 mg BID or volixibat 80 mg BID.

Study treatment dosing will begin on Day 1 and continue until end of the study treatment period, defined as the day of delivery. Study visits to assess safety, plasma concentrations of volixibat, pharmacodynamics, and efficacy will be conducted weekly from baseline until

delivery. Because alternative measures may be implemented when necessary for public health or other emergency situations, and when sufficient to help ensure the safety of study participants, some visits may be conducted as a home health or remote visit at the discretion of the investigator upon approval by the medical monitor or designee and in accordance with local and regional regulations (see Protocol Appendix 10). Participants will also enter ItchRO assessments into an electronic diary (eDiary) once daily. Use of limited rescue therapies for ICP will be permitted for participants who meet protocol-specified criteria.

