The null hypothesis of equal treatment effect will be rejected if the statistical analysis results in a 2-sided p-value for treatment at Week 3 is  $\leq 0.05$ . For each cohort, LS means will be calculated for each treatment group for each postbaseline visit in the model. The difference between volixibat and placebo change from baseline in sBA will be estimated, with the corresponding 2-sided 95% CI constructed for each visit through Week 3. The change from baseline LS means with standard error, 95% CI for the LS means, p-value for testing if the LS mean is zero, LS mean difference between treatment groups (volixibat minus placebo) with standard error, 95% CI for the LS mean difference, and p-value for testing if the treatment LS means are equal will be presented.

The study will be claimed successful if the hypothesis of no treatment effect on the primary efficacy endpoint over the primary cohort in the mITT population from Part 2 is rejected at the 0.05 (2-sided) significance level.

Summary statistics on total sBA by treatment group and visit will also be presented. In addition, a figure with the LS mean  $\pm$  standard error of change from baseline in total sBA will be presented by treatment group and visit.

In addition, a responder analysis (based on change in total sBA) may be considered.

Separately, a similar analysis on the open-label supplemental cohort will be performed. The analysis will be identical, except that baseline sBA will not be a covariate used within the model.

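### The open-label Part 1 sBA model leaves out baseline sBA without a stated reason, which may cost precision if the two dose arms are compared in one model

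*Protocol*

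**What the plan says.** **Protocol.** The Part 2 primary model in Section 10.4.1.1 adjusts for baseline: "The MMRM model will include the fixed, continuous effects of baseline sBA and gestational age". It also contains gestational diabetes, treatment, visit and their interaction. The same section, and the Synopsis, then carry the model over to each open-label cohort: "The analysis will be identical, except that baseline sBA will not be a covariate used within the model". The between-group output of the model is described as "LS mean difference between treatment groups (volixibat minus placebo) with SE", and Part 1 has no placebo arm.

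Part 1 randomizes up to 80 participants 1:1 to 20 mg or 80 mg. Criterion 4 of Section 5.1 requires sBA of at least 10 µmol/L "as assessed by the central laboratory during the screening period or local laboratory at any time during the current pregnancy" and sets no ceiling. Section 6.3.1 stratifies Part 1 on UDCA use, gestational age and gestational diabetes, not on sBA. Section 10 requires Part 1 efficacy to be summarized separately by baseline UDCA use. Section 10.1 describes Part 1 as estimation without formal testing. Section 10.4.4 says that it informs dose selection and the Part 2 sample size.

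**SAP.** Section 1 states: "This SAP is based on the study protocol Version 1, 14 October 2020". Section 6.1.2 has the same exception, but for a different group: "Separately, a similar analysis on the open-label supplemental cohort will be performed". Section 1.2 defines that group by a narrow band, 15 to below 20 µmol/L: "Supplemental cohort: Up to 30 participants with ICP with screening sBA level from". Section 3.3 gives the general rule: "For efficacy endpoints, the baseline value of the efficacy variable(s) will be included as a covariate in the efficacy analysis model".

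**The concern.** Baseline sBA is the covariate most directly tied to change in sBA, and it is already collected on Day 0. Part 2 both balances allocation on highest sBA and adjusts for baseline sBA. Part 1 does neither, although its sBA range is open at the top. A chance baseline difference between the dose arms would be left in the estimate. Variation in change that baseline could explain would stay in the error term.

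What is at stake is the width of an interval in a descriptive analysis that is one input to dose selection and Part 2 sizing. Change in sBA to Week 3 is a listed endpoint in its own right for Part 2 only (Protocol Section 3.1). Among the endpoints shared with Part 1, it appears only within an association endpoint (Section 3.4).

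**Working it through.** **Inputs from the documents.** SD 25 and 20 per group (Protocol Section 10.1); a cap of 80 participants at 1:1, so 40 per arm (Synopsis); SAP Section 1.3 half-width of 16 for a two-arm difference at 20 per arm.

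**Assumption.** The documents give no correlation r between baseline sBA and change at Week 3. It is shown at absolute values of 0, 0.3, 0.5 and 0.7.

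**The plan's own figures.**
- One arm, n = 20: 1.96 × 25/√20 = 10.96, matching the protocol's 11.
- Difference, 20 per arm: t(0.975, 38) × 25 × √(2/20) = 2.024 × 7.906 = 16.0, matching the SAP's 16.

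**Dose difference without baseline sBA.** Half-width = t(0.975, 2n−2) × 25 × √(2/n).
- n = 40: 1.991 × 5.590 = 11.13
- n = 20: 2.024 × 7.906 = 16.00

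**Dose difference with baseline sBA.** Half-width = t(0.975, 2n−3) × 25 × √(2/n) × √(1−r²) × √(1 + 1/(2n−4)). The last factor is the average cost of estimating the slope. Example, n = 40 and r = 0.5: 1.991 × 5.590 × 0.866 × 1.0066 = 9.70.

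| Per arm | Without | r = 0 | r = 0.3 | r = 0.5 | r = 0.7 |
|---|---|---|---|---|---|
| 40 | 11.13 | 11.20 | 10.69 | 9.70 | 8.00 |
| 20 | 16.00 | 16.24 | 15.49 | 14.06 | 11.60 |

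At r = 0 the interval is wider by 11.20/11.13, about 0.7%, at 40 per arm and by 16.24/16.00, about 1.5%, at 20 per arm. The two widths are equal at r of about 0.12 and 0.17 respectively. Simulation of a single-time-point analysis of covariance agreed with these figures.

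**Arm means.** In a joint model, with each arm evaluated at the overall baseline mean, the variance factor is 1 − r²/2, so the gain is half as large. At 20 per arm the half-width is 10.96, 10.71, 10.25 and 9.52 for the four values of r, before a slope-estimation cost of at most 0.7%. In a separate fit per arm with complete data, the LS mean at the arm's own baseline mean is the raw arm mean, so there is essentially no gain.

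**The SAP's narrow cohort.** A variable confined to a 5 µmol/L range has variance of at most 2.5² = 6.25, which is 6.25/625 = 1.0% of the variance of change. If the slope is at most 1 in size and Day 0 sBA stays in the screening range, baseline could explain at most about 1% there. The exception cost almost nothing in that cohort.

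**The case against.** **The dose difference is never written out.** The sentence concerns each open-label cohort. Protocol Section 4.3.1 uses the word cohorts for the 20 mg and 80 mg groups, and Section 10.1 frames Part 1 precision as an interval for each arm's mean. On that reading the model is fitted per dose arm and the gain disappears. This stands as a limit on the point. The instruction that the analysis be otherwise identical does support a between-arm term, so the text is ambiguous and should be settled.

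**A reader might infer that the SAP contradicts itself.** Section 3.3 is a general rule and Section 6.1.2 a specific exception for a named cohort; a specific exception normally governs. Both were written for protocol Version 1, so neither settles the current Part 1.

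**A reader might also infer that the sentence was copied from the old cohort by mistake.** The shared wording makes this plausible, but no document says so, or says that the narrow range was the reason for the exception. What can be said is that the current Part 1 population is not that cohort.

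**The gain is unknown.** It depends on r. The planned model already holds gestational age and gestational diabetes, so strictly the partial correlation matters. In small UDCA subsets the cost also grows: at an assumed 10 per arm, the same formula gives an interval about 3.5% wider at r = 0, with break-even near r = 0.26. All of this stands.

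**Conclusion.** The point holds as a low-priority improvement. The protocol drops baseline sBA from the open-label model without a reason, in a population with no sBA ceiling and no stratification on sBA. If both dose arms are in one model, the half-width of the Week 3 difference changes by between +0.7% and −28% at 40 per arm, and between +1.5% and −27.5% at 20 per arm, for r from 0 to 0.7. These figures rest on an SD of 25, complete data, a single-time-point approximation to the MMRM and an assumed r.

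It would be too strong to conclude that the Part 1 dose comparison is biased or that the trial's conclusions are at risk. With complete data the unadjusted randomized contrast is unbiased. Dose selection rests on a wider review of dose, exposure and response (Protocol Section 4.4). Part 1 is not combined with Part 2 for inference, and the Part 2 model keeps baseline sBA.

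**What to change.** 1. Delete the exception in the Synopsis and in Protocol Section 10.4.1.1.
2. State that Part 1 is fitted as one MMRM with both dose arms: change in total sBA through Week 3, with baseline sBA, gestational age, gestational diabetes, background UDCA use (a Part 1 stratification factor), dose arm, visit and dose arm-by-visit.
3. Report each arm's LS mean change and the 80 mg minus 20 mg difference at Week 3 with 95% CI, as estimation only, in place of the placebo contrast, which cannot apply to Part 1. Present these alongside the separate UDCA summaries that Section 10 requires.
4. When the SAP is brought up to the current protocol, do not carry the Section 6.1.2 exception over to Part 1.

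If the sponsor prefers to keep the exception, the protocol should give the reason and say whether the arms are fitted jointly or separately.

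**Cost.** Wording, and about one degree of freedom for baseline sBA; the UDCA term uses one more. No new data are needed. If baseline is unrelated to change, the interval is up to about 0.7% (40 per arm) or 1.5% (20 per arm) wider, and more in smaller UDCA subsets.
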